In subjects receiving sunitinib for treatment-naive MRCC, 39% had bleeding events compared with 11% receiving IFN-α (Investigator's Brochure, 2014). Treatment emergent bleeding events occurred in 18% of patients receiving sunitinib in the double-blind treatment phase of the GIST phase 3 study, compared with 17% receiving placebo. Seventeen (4.5%) patients on sunitinib versus 5 (1.7%) patients on IFN-α experienced Grade 3 or greater treatmentrelated bleeding events. Of patients receiving sunitinib for cytokine-refractory MRCC (C-R MRCC), 26% experienced bleeding. Bleeding events, excluding epistaxis, occurred in 21.7% of patients receiving sunitinib in the Phase 3 pNET study compared to 9.85% of patients receiving placebo. Routine assessment of this event should include complete blood counts and physical examination. Among 516 patients enrolled in CDUS-monitored trials with sunitinib alone or in combination with other agents, there were 123 reported bleeding events (CDUS data). Epistaxis was the most common hemorrhagic AE reported. Tumor-related hemorrhage can occur with sunitinib and in the case of pulmonary tumors, may present as severe and life-threatening hemoptysis or pulmonary hemorrhage.

EAY131-V

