Rev. Add13 Rev. Add25	2.	1.2	Patients must have a somatic cKIT mutation in exon 9, 11, 13 or 14, excluding exon 17 or 18 mutations, activating PDGFRA or PDGFRB variants and fusions, or another aberration, as identified via the MATCH Master Protocol and described in Appendix II. See Appendix II	
			Actionable Mutations of Interest (aMOIs)for information on the inclusion and exclusion mutations, along with the corresponding Levels of Evidence (LOE).	
	2.	1.3	Patient must have normal organ and marrow function as defined below: Total bilirubin must be within normal institutional limits. Creatinine must be within normal institutional limits. OR	

		Creatinine clearance \geq 60 mL/min/1.73 m ² for patients with creatinine levels above institutional normal.
		Creatinine Clearance:
		 Serum Calcium must be ≤ 12.0 mg/dL.
	2.1.4	Patients must have an electrocardiogram (ECG) within 8 weeks prior to treatment assignment and must have no clinically important abnormalities in rhythm, conduction or morphology of resting ECG (e.g. complete left bundle branch block, third degree heart block):
		Date of ECG:
Rev. 2/16	2.1.5	Patients with known left ventricular dysfunction must have ECHO or a nuclear study (MUGA or First Pass) within 4 weeks prior to registration to treatment and must not have left ventricular ejection fraction (LVEF) < institutional lower limit of normal (LLN). If the LLN is not defined at a site, the LVEF must be > 50% for the patient to be eligible.
		2.1.5.1 The following groups of patients are eligible provided they have New York Heart Association Class II cardiac function on baseline ECHO/nuclear study:
		 Patients with a history of Class II heart failure who are asymptomatic on treatment
		 Patients with prior anthracycline exposure
		 Patients who have received central thoracic radiation that included the heart in the radiotherapy port
		Date of ECHO/nuclear study:
		NOTE: Pre-treatment LVEF determination in patients without known left ventricular dysfunction (or per Section 2.1.5.1) is NOT otherwise required.
	2.1.6	Patients with any of the following conditions are excluded:
		 Serious or non-healing wound, ulcer, or bone fracture
		 History of abdominal fistula, gastrointestinal perforation, or intra- abdominal abscess within 28 days of treatment
		 Any history of cerebrovascular accident (CVA) or transient ischemic attack within 12 months prior to study entry

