		 History of myocardial infarction, cardiac arrhythmia, stable/unstable angina, symptomatic congestive heart failure, or coronary/peripheral artery bypass graft or stenting within 12 months prior to study entry
		 History of pulmonary embolism within the past 12 months
	2.1.7	Patients must not have known hypersensitivity or excess toxicity from sunitinib or compounds of similar chemical composition or biologic effect. This list includes, but is not limited to, patients with significant cardiac or hepatic toxicity from multikinase inhibitors with similar kinase inhibitory profiles (sorafenib, regorafenib, pazopanib).

	NCI Update Date: August 12, 2015
	Questions regarding a significant intolerance to a prior therapy should be directed to the sub-protocol PI.
2.1.8	Patients must not have had prior therapy with sunitinib.
2.1.9	Patients must not have planned ongoing administration of STRONG and MODERATE CYP3A4 inhibitors or inducers. See Appendix V (and Appendix VI of the MATCH Master Protocol). The reference list of cytochrome p450 (CYP) isozymes and classification of strong, moderate, and weak interactions is available through the FDA website:
	http://www.fda.gov/Drugs/DevelopmentApprovalProcess/Development
	Resources/DrugInteractionsLabeling/ucm093664.htm
	 Strong CYP3A4 inhibitors are not permitted within 7 days before dosing and should be avoided throughout the study.
	 Strong CYP3A4 inducers are not permitted within 12 days before dosing and should be avoided throughout the study.
2.1.10	Patients must not have GIST, renal cell carcinoma, or pancreatic neuroendocrine tumor
2.1.11	Patients must not have a NCI CTCAE version 4 grade 3 hemorrhage within 4 weeks of starting study treatment
2.1.12	Patients must not have hypertension that cannot be controlled by medications (> 140/90 mmHg despite optimal medical therapy)
2.1.13	Patients must not have pre-existing thyroid abnormality with thyroid function that cannot be maintained in the normal range with medication
2.1.14	Participants may not have a major surgical procedure, open biopsy, or significant traumatic injury within 28 days prior to starting sunitinib.
2.1.15	Patients with known brain metastases should be excluded from this clinical trial because of their poor prognosis and because they often develop progressive neurologic dysfunction that would confound the evaluation of neurologic and other adverse events.

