METABOLISM AND NUTRITION DISORDERS - Hypercalcemia; Hyperglycemia; Hyperkalemia; Hypokalemia; Hyponatremia

MUSCULOSKELETAL AND CONNECTIVE TISSUE DISORDERS - Bone pain

NERVOUS SYSTEM DISORDERS - Cognitive disturbance; Peripheral sensory neuropathy; Seizure; Spinal cord compression; Syncope

PSYCHIATRIC DISORDERS - Anxiety; Confusion

RENAL AND URINARY DISORDERS - Hematuria; Urinary retention

REPRODUCTIVE SYSTEM AND BREAST DISORDERS - Hematosalpinx

¹This table will be updated as the toxicity profile of the agent is revised. Updates will be distributed to all Principal Investigators at the time of revision. The current version can be obtained by contacting [contact]. Your name, the name of the investigator, the protocol and the agent should be included in the e-mail.

²Gastrointestinal perforation includes Colonic perforation, Duodenal perforation, Esophageal perforation, Gastric perforation, Ileal perforation, Jejunal perforation, Rectal perforation, and Small intestinal perforation under the GASTROINTESTINAL DISORDERS SOC.

³Allergic reactions observed include anaphylaxis and angioedema.

⁴The majority of hemorrhage events were mild. Major events, defined as symptomatic bleeding in a critical area or organ (e.g., eye, GI tract, GU system, respiratory tract, nervous system [including fatal intracranial hemorrhage, and cerebrovascular accident], and tumor site) have been reported.

EAY131-V Version Date: November 10, 2022

NCI Update Date: August 12, 2015

RESPIRATORY, THORACIC AND MEDIASTINAL DISORDERS - Pharyngolaryngeal pain; Pleural effusion; Pneumothorax

VASCULAR DISORDERS - Flushing; Hypotension

Rev.2/16 **NOTE**:

Sunitinib malate (SU011248 L-malate) in combination with other agents could cause an exacerbation of any adverse event currently known to be caused by the other agent, or the combination may result in events never previously associated with either agent.

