Grade 3 or 4 AST or ALT increase	 Hold sunitinib If no alternative explanation for transaminitis can be determined (such as viral hepatitis, progressive underlying hepatic malignancy), discontinue sunitinib Otherwise, upon resolution to ≤ grade 1 or baseline, re-start sunitinib at one dose-reduction step If patient develops ≥ grade 3 hepatic failure, discontinue sunitinib.
Grade 3 or 4 electrocardiogram QT corrected interval prolonged	 See also Section 3.5.4. Hold sunitinib Check and immediately administer potassium to achieve levels of ≥ 4 mmol/L and magnesium to levels of ≥ 2 mg/dL Consider chronic oral supplementation of potassium and/or magnesium Review with the subprotocol principal investigator and consult with a cardiologist prior to patient's next scheduled treatment, considering the following options: HOLD sunitinib until QTc recovers to pre-study treatment baseline (grade 1 or less, or ≤ 480ms) When QTc returns to baseline, reinitiate sunitinib cautiously, with additional QTc monitoring at earliest possible follow-up opportunity, but no more than 8 days from reintroduction of sunitinib If QTc prolongation event felt attributable to sunitinib, follow protocol dose-reduction-step guidelines (see table above in Section 3.4) when re-introduced For recurrent QTc grade 3 felt attributable to sunitinib despite dose-step reduction, discontinue sunitinib

EAY131-V
Version Date: November 10, 2022
NCI Update Date: August 12, 2015

	Monitor urine protein once every cycle with urinalysis. If protein excretion positive on urinalysis, obtain 24-hour urine protein.
Proteinuria	Interrupt treatment for 24-hour urine protein ≥ 3 grams. Discontinue for repeat episodes of protein ≥ 3 grams despite dose reductions or nephrotic syndrome.
Nervous System Disorders (poter	

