Grade 2 pre-syncope or grade 3 syncope	 See also Section 3.5.2. Obtain ECG for cardiology review/consultation Check magnesium and potassium and promptly administer potassium to achieve level of ≥ 4 mmol/L and magnesium to level ≥ 2 mg/dL IF ECG shows new dysrhythmia or QTc ≥ grade 2 (> 480ms), hospitalize for monitoring with cardiology consultation HOLD sunitinib until any potassium and magnesium abnormalities are corrected, symptoms resolved and QTc returns to grade 1 or less (≤ 480ms) Reintroduce sunitinib cautiously, with input from cardiology and with additional QTc evaluation, either concurrent with reintroduction or at earliest possible follow-up opportunity and no more than 8 days from reintroduction If event felt attributable to sunitinib consider dose modification of sunitinib when re-introduced Consider chronic oral supplementation of potassium and/or magnesium For recurrent syncope or near-syncope felt attributable to sunitinib consider permanent discontinuation
All Other Non-Hematologic Toxici	ties Attributable to sunitinib
Any grade 2 non-hematologic toxicity that is persistent, intolerable, or unresponsive to optimal management	At the treating investigator's discretion, reduce to the next lower dose-reduction step
Grade 3 or 4	 Omit sunitinib until resolution to ≤ grade 1, baseline or tolerable grade 2 Re-start sunitinib at one dose-reduction step If AE persists > 14 days, discontinue sunitinib In addition, at investigator discretion: For bleeding that requires more than minor medical intervention, consider discontinuing sunitinib For severe persistent hypertension or hypertensive crisis despite optimal antihypertensive management, consider discontinuing sunitinib For evidence of cardiac ischemia or myocardial infarction, consider discontinuing sunitinib For grade 4 AEs related to sunitinib, consider discontinuing sunitinib

NCI Update Date: August 12, 2015

Dose reduction guideline table for Plantar Palmar Erythrodysesthesia

Table 2. Sunitinib Dose-Reduction Guidelines and Management for PPE

Grade	Occurrence	Action
Grade 1	1 st occurrence or recurrence	Continue sunitinib and institute supportive measures for symptomatic relief.*
Grade 2: Moderate and painful skin changes of hands and/or feet such as peeling, blisters, bleeding,	1 st or 2 nd occurrence	Continue sunitinib and institute supportive measures for symptomatic relief.* If no improvement within 7 days, see below.

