hyperkeratosis, erythema, swelling; and/or any such changes that are limiting instrumental activities of daily living (preparing meals, shopping for groceries, using the telephone, managing money, etc)	No improvement within 7 days or recurrence beyond 2 nd occurrence	Stop sunitinib treatment until toxicity resolves to grade 0-1. When resuming treatment, decrease sunitinib dose by 1 dose-reduction step.
	Coourtenee	Institute supportive measures for symptomatic relief.*
Grade 3: Severe and painful skin changes of the hands and/or feet, such as moist desquamation, ulceration, blistering, bleeding, hyperkeratosis, erythema, swelling;	1 st or 2 nd occurrence	Stop sunitinib treatment until toxicity resolves to grade 0-1. When resuming treatment, decrease s sunitinib by 1 dose-reduction step.
and/or any such severe changes or pain that are limiting self-care		Institute supportive measures for symptomatic relief.*
activities of daily living (bathing, dressing, feeding self, using toilet, taking medications or becoming bedridden)	3 rd occurrence	Discontinue sunitinib treatment.

^{*}See section 3.5.3 for PPE management

Table 3. Other Hematologic and Non-Hematologic Adverse Events

Event	AE Grade or Observation	Dose modification
	Grades 1 and 2	Maintain dose
Neutropenia	Grade 3*	Hold sunitinib until ≤ grade 2, then resume at same dose level
	Grade 4	Hold sunitinib until ≤ grade 2, then reduce 1 dose level and resume treatment
	Grades 1 and 2	Maintain dose
Thrombocytopenia	Grade 3* and severe grade 2, at investigator discretion	Hold sunitinib until ≤ grade 2, then reduce 1 dose level and resume treatment
	Grade 4	Hold sunitinib until ≤ grade 2, then reduce 1 dose level and resume treatment

^{*}Recurrent grade 3 events require dose reduction.

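### Criterion 2.1.11 excludes a recent grade 3 hemorrhage but, as worded, not a more severe grade 4 one

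*Protocol*

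**What the plan says.** The eligibility checklist in Section 2.1 contains one criterion on bleeding, 2.1.11: "Patients must not have a NCI CTCAE version 4 grade 3 hemorrhage within 4 weeks of starting study treatment".

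The preamble to Section 2 requires every listed criterion to be met, allows no waivers, and lets a signed checklist serve as source documentation. It adds that registering someone who fails a criterion can lead to removal from the analysis and to a major violation at audit. Criterion 2.1.1 also imports Section 3.1 of the MATCH Master Protocol, apart from its item 3.1.6.

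The protocol addresses bleeding in three other places:

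- The Safety Profile in Section 1.1 reports the numbers of patients who "experienced Grade 3 or greater treatmentrelated bleeding events". It warns that tumor-related bleeding with pulmonary tumors "may present as severe and life-threatening hemoptysis or pulmonary hemorrhage".
- Footnote 4 to the adverse event list in Section 3.3 says most hemorrhages were mild but that serious ones have been reported: "Major events, defined as symptomatic bleeding in a critical area or organ", with the tumor site among its examples.
- Table 1 in Section 3.4 has a general row for other non-hematologic toxicity of grade 3 or 4. Within it, at the investigator's discretion: "For bleeding that requires more than minor medical intervention, consider discontinuing sunitinib".

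**The concern.** An exclusion based on severity should cover everything at or above its threshold. Criterion 2.1.11 gives a single value. Taken at its word, it turns away the patient with the less severe bleed and is silent on the patient with the more severe one.

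Sites work through the checklist item by item. A site could truthfully mark 2.1.11 as satisfied for someone with a grade 4 bleed two weeks earlier. The stake is patient safety: such a patient would start a drug that the protocol itself links to life-threatening hemorrhage. Nothing obliges an investigator to enrol that patient, and questions can go to the Group's officers, but a safety exclusion should not depend on either.

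**Working it through.** No arithmetic applies, because the point concerns the wording of one criterion. The check has four parts.

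**1. Does another printed criterion cover a recent grade 4 bleed?** Of the 16 criteria, only 2.1.11 names hemorrhage (1 of 16). These items catch some cases:

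| Criterion | What it can catch |
|---|---|
| 2.1.6 | "Serious or non-healing wound, ulcer, or bone fracture"; gastrointestinal perforation within 28 days; cerebrovascular accident within 12 months |
| 2.1.14 | Bleeding tied to major surgery or significant trauma within 28 days |
| 2.1.15 | Patients with known brain metastases |
| 2.1.16 | Patients on therapeutic coumarin anticoagulants |

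A spontaneous grade 4 pulmonary or tumor-site bleed in a patient with none of these conditions is covered by no printed item.

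**2. Does a bare grade 3 mean a floor in this document?** Usage is mixed.

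- *Range written out:* Section 1.1 reports bleeding as grade 3 or greater. Table 1 has rows headed grade 3 or 4 and sets a threshold of grade 3 and above for hepatic failure.
- *Bare grade 3, exact:* the neutropenia entry in Table 3 says for grade 3: "Hold sunitinib until ≤ grade 2, then resume at same dose level". Grade 4 has its own row, with a dose reduction.
- *Bare grade 3, evidently a floor:* the QTc entry in Table 1 says "For recurrent QTc grade 3 felt attributable to sunitinib despite dose-step reduction, discontinue sunitinib". It sits in a row for grades 3 and 4, and a recurrence at grade 4 could hardly be treated more leniently.

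The bare form is therefore ambiguous here, and usage elsewhere does not settle how to read 2.1.11.

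**3. Could a comparison sign have been lost when the PDF was read?** Six survive in Section 2: creatinine clearance, serum calcium, two for ejection fraction, blood pressure and INR. The sentence in 2.1.11 also reads as complete without one. A lost sign is unlikely but not excluded.

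**4. Is the entry rule consistent with the on-treatment rule?** Under Table 1, a grade 4 bleed attributed to sunitinib requires the drug to be withheld, and discontinuation is to be considered. An entry criterion silent on that grade does not fit with this.

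**The case against.** The strongest case against the point has four parts.

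- **No gap in enrolment is shown.** Master Protocol Section 3.1 also governs entry and is not available, so whether a patient with a recent grade 4 bleed could be registered cannot be determined. This stands and limits the claim to the printed text of Section 2.
- **The harmful reading is implausible.** Few physicians would conclude that a worse bleed is acceptable. History and physical examination, performance status and blood counts are required before registration, and eligibility questions go to the Group's officers. This also stands and makes harm unlikely, but none of those assessments carries a bleeding threshold.
- **Usage elsewhere is thin evidence.** The Section 1.1 wording is background reporting. The Table 1 row is generic, and its bleeding item is defined by the intervention needed, not by grade. Neutropenia grade 3 is exact only because a grade 4 row follows it. This is fair: only Section 1.1 attaches a grade specifically to bleeding. The point does not rest on usage, though, because the words of 2.1.11 are themselves incomplete.
- **It is copy-editing.** The change should alter practice little, and no statistical quantity moves. The second half is right. But the defect lies in an operative safety exclusion rather than in background text, so it merits more than an editorial note.

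**Conclusion.** The concern holds as a drafting defect of modest severity in a safety criterion. As printed, 2.1.11 bars a grade 3 hemorrhage within four weeks and does not bar a grade 4 one, and no other criterion from 2.1.1 to 2.1.16 does so in general.

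The conclusion rests on the literal wording and assumes that no sign was lost from the source PDF. It does not claim that such a patient would in the end be enrolled, since the Master Protocol may exclude them. The number affected among the 35 planned patients cannot be derived from the document. Sample size, error rates and the analysis are unaffected.

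**What to change.** In 2.1.11, insert 'or higher' after 'grade 3' (or write the threshold as ≥ grade 3) and leave the four-week window as it is.

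The cost is one phrase in the next amendment and the same change on the checklist. It adds no test, visit or form, and it removes only patients whom the criterion very likely already meant to exclude.

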3.1.1 Sunitinib

50mg po, daily, for 4 weeks continuously, followed by 2 weeks of rest. Repeat at 6 week cycles until progression or patient is withdrawn from study, as outlined in Section 3.6.

3.1.2 Dose interruptions and modifications will be performed according to guidelines outlined in Section 3.4

3.2 Adverse Event Reporting Requirements

The Adverse Event Reporting Requirements for all EAY131 subprotocols are outlined in the MATCH MASTER protocol. Please refer to those guidelines when determining if an event qualifies as a Serious Adverse Event (SAE) and requires expedited reporting via CTEP's Adverse Event Reporting System (CTEP-AERS).

In addition, the following section outlines agent specific requirements and must be followed to ensure all reporting requirements are met.

3.2.1 Additional instructions, requirements and exceptions for protocol EAY131 – Subprotocol V

Additional Instructions

For instructions on how to specifically report events that result in persistent or significant disability/incapacity, congenital anomaly, or birth defect events via CTEP-AERS, please contact the AEMD Help Desk at [contact] or [contact]. This will need to be discussed on a case-by-case basis.

EAY131 – Subprotocol V specific expedited reporting requirements:

• **Pregnancies**: Pregnancies and suspected pregnancies (including a positive or inconclusive pregnancy test, regardless of age or disease state) occurring while the female patient is on Sunitinib, or within 28 days of the female patient's last dose of Sunitinib, are considered immediately reportable events. The pregnancy, suspected pregnancy, or positive/ inconclusive pregnancy test must be reported via CTEP-AERS within 24 hours of the Investigator's knowledge. Please refer to Appendix VIII in MATCH Master Protocol for detailed instructions on how to report the occurrence of a pregnancy as well as the outcome of all pregnancies.

Rev Add25

EAY131 – Subprotocol V specific expedited reporting exceptions:

For Subprotocol V, the adverse events listed below **do not** require expedited reporting via CTEP-AERS:

 If an AE meets the reporting requirements of the protocol, and it is listed on the SPEER, it should ONLY be reported via CTEP-AERS if the grade being reported exceeds the grade listed in the parentheses next to the event

3.2.2 Second Primary Cancer Reporting Requirements

All cases of second primary cancers, including acute myeloid leukemia (AML) and myelodysplastic syndrome (MDS), that occur following treatment on NCI-sponsored trials must be reported to ECOG-ACRIN using Medidata Rave

- A second malignancy is a cancer that is UNRELATED to any prior anti-cancer treatment (including the treatment on this protocol). Second malignancies require ONLY routine reporting as follows:
 - 1. Complete a Second Primary Form in Medidata Rave within 14 days.
 - 2. Upload a copy of the pathology report to ECOG-ACRIN via Medidata Rave confirming the diagnosis.
 - 3. If the patient has been diagnosed with AML/MDS, upload a copy of the cytogenetics report (if available) to ECOG-ACRIN via Medidata Rave.
- A secondary malignancy is a cancer CAUSED BY any prior anticancer treatment (including the treatment on this protocol).
 Secondary malignancies require both routine and expedited reporting as follows:
 - Complete a Second Primary Form in Medidata Rave within 14 days
 - 2. Report the diagnosis via CTEP-AERS at http://ctep.cancer.gov
 Report under a.) leukemia secondary to oncology chemotherapy, b.) myelodysplastic syndrome, or c.) treatment related secondary malignancy
 - 3. Upload a copy of the pathology report to ECOG-ACRIN via Medidata Rave and submit a copy to NCI/CTEP confirming the diagnosis.
 - 4. If the patient has been diagnosed with AML/MDS, upload a copy of the cytogenetics report (if available) to ECOG-ACRIN via Medidata Rave and submit a copy to NCI/CTEP.

NOTE: The Second Primary Form and the CTEP-AERS report should not be used to report recurrence or development of metastatic disease.

NOTE: If a patient has been enrolled in more than one NCI-

sponsored study, the Second Primary Form must be submitted for the most recent trial. ECOG-ACRIN must be provided with a copy of the form and the associated pathology report and cytogenetics report (if available) even if ECOG-ACRIN was not the patient's most recent trial.

NOTE: Once data regarding survival and remission status are no

longer required by the protocol, no follow-up data should be submitted via CTEP-AERS or by the Second Primary

Form.

NCI Update Date: August 12, 2015

Rev. 5/16 Rev. 3/17 Rev. Add21

3.3 Comprehensive Adverse Events and Potential Risks List (CAEPR) for Sunitinib malate (SU011248 L-malate, NSC 736511).

The Comprehensive Adverse Events and Potential Risks list (CAEPR) provides a single list of reported and/or potential adverse events (AE) associated with an agent using a uniform presentation of events by body system. In addition to the comprehensive list, a subset, the Specific Protocol Exceptions to Expedited Reporting (SPEER), appears in a separate column and is identified with bold and italicized text. This subset of AEs (SPEER) is a list of events that are protocol specific exceptions to expedited reporting to NCI (except as noted below). Refer to the 'CTEP, NCI Guidelines: Adverse Event Reporting Requirements' http://ctep.cancer.gov/protocolDevelopment/electronic applications/docs/aeguidelines.pdf for further clarification. *Frequency is provided based on 7115 patients*. Below is the CAEPR for Sunitinib malate (SU011248 L-malate).

NOTE:

If an AE meets the reporting requirements of the protocol, and it is listed on the SPEER, it should ONLY be reported via CTEP-AERS if the grade being reported exceeds the grade listed in the parentheses next to the event in the SPEER.

Version 2.14, February 15, 2019¹

	2.17, 1 obludiy 10, 2010		
Relationshi	Specific Protocol Exceptions to Expedited Reporting (SPEER)		
Likely (>20%)	Less Likely (<=20%)	Rare but Serious (<3%)	
BLOOD AND LYMPH	ATIC SYSTEM DISORDI	ERS	
	Anemia		Anemia (Gr 3)
		Hemolytic uremic syndrome	
		Thrombotic thrombocytopenic purpura	
CARDIAC DISORDE	RS		
		Cardiac disorders - Other (cardiomyopathy)	
		Heart failure	
		Left ventricular systolic dysfunction	
		Myocardial infarction	
ENDOCRINE DISOR	RDERS		
		Endocrine disorders - Other (thyroiditis)	
		Hyperthyroidism	
	Hypothyroidism		Hypothyroidism (Gr 2)
EYE DISORDERS			
		Eye disorders - Other (macular edema)	Eye disorders - Other (macular edema) (Gr 2)
	Papilledema		Papilledema (Gr 2)
		Vision decreased	Vision decreased (Gr 2)

Relationsh	Specific Protocol Exceptions to Expedited Reporting (SPEER)				
Likely (>20%)		Rare but Serious (<3%)			
GASTROINTESTINA	AL DISORDERS	T			
	Abdominal distension		Abdominal distension (Gr 2)		
Abdominal pain			Abdominal pain (Gr 3)		
Anal mucositis			Anal mucositis (Gr 2)		
Constipation			Constipation (Gr 2)		
Diarrhea			Diarrhea (Gr 3)		
	Dry mouth		Dry mouth (Gr 2)		
Dyspepsia			Dyspepsia (Gr 2)		
	 	Esophagitis			
	Flatulence		Flatulence (Gr 2)		
	Gastritis		Gastritis (Gr 2)		
	Gastroesophageal reflux disease				
		Gastrointestinal perforation ²			
Mucositis oral			Mucositis oral (Gr 3)		
Nausea			Nausea (Gr 3)		
	Oral pain		Oral pain (Gr 2)		
	·	Pancreatitis			
Rectal mucositis			Rectal mucositis (Gr 2)		
Small intestinal mucositis			Small intestinal mucositis (Gr 2)		
Vomiting			Vomiting (Gr 3)		
	_ ERS AND ADMINISTRATI	ON SITE CONDITIONS	Volinting (Gr 3)		
GENERAL DISORD	Chills	I CONDITIONS	Chills (Gr 2)		
	Edema limbs		Edema limbs (Gr 2)		
Ectique	Edema iimbs		Fatigue (Gr 3)		
Fatigue	Fover		 		
	Fever Flu like symptoms		Fever (Gr 2)		
	Fiu like symptoms		Non covding about nain		
	Non-cardiac chest pain		Non-cardiac chest pain (Gr 2)		
HEPATOBILIARY D	ISORDERS				
		Cholecystitis			
		Hepatic failure			
IMMUNE SYSTEM I	IMMUNE SYSTEM DISORDERS				
		Allergic reaction ³			
INFECTIONS AND I					
		Infections and infestations - Other (necrotizing fasciitis)			
INJURY, POISONIN	IG AND PROCEDURAL CO	OMPLICATIONS			
		Wound complication			

Relationshi	Specific Protocol Exceptions to Expedited Reporting (SPEER)		
Likely (>20%)	Less Likely (<=20%)	Rare but Serious (<3%)	
INVESTIGATIONS			
	Alanine aminotransferase increased		Alanine aminotransferase increased (Gr 3)
	Alkaline phosphatase increased		Alkaline phosphatase increased (Gr 2)
	Aspartate aminotransferase increased		Aspartate aminotransferase increased (Gr 3)
	Blood bilirubin increased		Blood bilirubin increased (Gr 2)
	CPK increased		Over the land
	Creatinine increased	Electrocardiogram QT corrected interval prolonged	Creatinine increased (Gr 3)
	Lipase increased		Lipase increased (Gr 4)
	Lymphocyte count		Lymphocyte count
	decreased		decreased (Gr 2)
	Neutrophil count decreased		Neutrophil count decreased (Gr 4)
	Platelet count		Platelet count decreased
	decreased		(Gr 4)
	Serum amylase increased		Serum amylase increased (Gr 2)
	Weight loss		Weight loss (Gr 2)
	White blood cell decreased		White blood cell decreased (Gr 3)
	NUTRITION DISORDERS		
Anorexia	5		Anorexia (Gr 3)
	Dehydration		Dehydration (Gr 3)
	Hyperuricemia		Hyperuricemia (Gr 2)
	Hypoalbuminemia		Hypoalbuminemia (Gr 2)
	Hypocalcemia	Hypoglypomia	
	Hypophosphatemia	Hypoglycemia	Hypophosphatemia (Gr 2)
	гурорноэрнасина	Tumor lysis syndrome	
MUSCUL OSKELETA	L AL AND CONNECTIVE TIS		
MOGGGEGGINEELT	Arthralgia	DOCE DICONDENCE	Arthralgia (Gr 2)
	Back pain		Back pain (Gr 2)
		Musculoskeletal and connective tissue disorder - Other (fistula formation)	
	Myalgia		Myalgia (Gr 2)
		Osteonecrosis of jaw	

Relationshi	Specific Protocol Exceptions to Expedited Reporting (SPEER)		
Likely (>20%)	Less Likely (<=20%)	Rare but Serious (<3%)	
	Pain in extremity	Rhabdomyolysis	Pain in extremity (Gr 2)
NEOPLASMS BENIC	GN, MALIGNANT AND UN	ISPECIFIED (INCL CYSTS	
AND TOLITO)		Leukemia secondary to oncology chemotherapy	
		Myelodysplastic syndrome	
NERVOUS SYSTEM	DISORDERS		
	Dizziness		
Dysgeusia			Dysgeusia (Gr 2)
	Headache		Headache (Gr 3)
		Leukoencephalopathy	
		Nervous system disorders - Other (cerebral infarction)	
	Paresthesia		
		Reversible posterior leukoencephalopathy syndrome	
		Transient ischemic attacks	
PSYCHIATRIC DISC	RDERS		
	Depression		
	Insomnia		Insomnia (Gr 2)
RENAL AND URINAL	RY DISORDERS		
		Acute kidney injury	
		Nephrotic syndrome	
		Proteinuria	
RESPIRATORY, THO	ORACIC AND MEDIASTIN	NAL DISORDERS	
	Cough		Cough (Gr 2)
	Dyspnea		Dyspnea (Gr 3)
	Epistaxis		Epistaxis (Gr 2)
Laryngeal mucositis			Laryngeal mucositis (Gr 2)
Pharyngeal mucositis			Pharyngeal mucositis (Gr 2)
Tracheal mucositis			Tracheal mucositis (Gr 2)
SKIN AND SUBCUTA	ANEOUS TISSUE DISOR	DERS	
	Alopecia		Alopecia (Gr 2)
	Dry skin		Dry skin (Gr 2)
		Erythema multiforme	
	Hair color changes		Hair color changes (Gr 2)
Palmar-plantar erythrodysesthesia syndrome			Palmar-plantar erythrodysesthesia syndrome (Gr 3)
	Pruritus Rash maculo-papular		Rash maculo-papular (Gr 3)

Adverse Events with Possible Specific Protocol Relationship to Sunitinib malate (SU011248 L-malate) **Exceptions to Expedited** (CTCAE 5.0 Term) Reporting (SPEER) [n= 7115] Less Likely (<=20%) Likely (>20%) Rare but Serious (<3%) Skin and subcutaneous tissue disorders - Other (pyoderma gangrenosum) Skin hypopigmentation Skin hypopigmentation (Gr 2) Stevens-Johnson syndrome Toxic epidermal necrolysis VASCULAR DISORDERS **Hypertension** Hypertension (Gr 3) Thromboembolic event Vascular disorders -Other (hemorrhage)4

Adverse events reported on Sunitinib malate (SU011248 L-malate) trials, but for which there is insufficient evidence to suggest that there was a reasonable possibility that Sunitinib malate (SU011248 L-malate) caused the adverse event:

BLOOD AND LYMPHATIC SYSTEM DISORDERS - Febrile neutropenia

CARDIAC DISORDERS - Atrial fibrillation; Cardiac arrest; Pericardial effusion

GASTROINTESTINAL DISORDERS - Ascites; Dysphagia; Gastrointestinal disorders - Other (enteritis); Hemorrhoids; Ileus; Small intestinal obstruction

GENERAL DISORDERS AND ADMINISTRATION SITE CONDITIONS - Pain

INVESTIGATIONS - GGT increased; INR increased

METABOLISM AND NUTRITION DISORDERS - Hypercalcemia; Hyperglycemia; Hyperkalemia; Hypokalemia; Hyponatremia

MUSCULOSKELETAL AND CONNECTIVE TISSUE DISORDERS - Bone pain

NERVOUS SYSTEM DISORDERS - Cognitive disturbance; Peripheral sensory neuropathy; Seizure; Spinal cord compression; Syncope

PSYCHIATRIC DISORDERS - Anxiety; Confusion

RENAL AND URINARY DISORDERS - Hematuria; Urinary retention

REPRODUCTIVE SYSTEM AND BREAST DISORDERS - Hematosalpinx

¹This table will be updated as the toxicity profile of the agent is revised. Updates will be distributed to all Principal Investigators at the time of revision. The current version can be obtained by contacting [contact]. Your name, the name of the investigator, the protocol and the agent should be included in the e-mail.

²Gastrointestinal perforation includes Colonic perforation, Duodenal perforation, Esophageal perforation, Gastric perforation, Ileal perforation, Jejunal perforation, Rectal perforation, and Small intestinal perforation under the GASTROINTESTINAL DISORDERS SOC.

³Allergic reactions observed include anaphylaxis and angioedema.

⁴The majority of hemorrhage events were mild. Major events, defined as symptomatic bleeding in a critical area or organ (e.g., eye, GI tract, GU system, respiratory tract, nervous system [including fatal intracranial hemorrhage, and cerebrovascular accident], and tumor site) have been reported.

EAY131-V Version Date: November 10, 2022

NCI Update Date: August 12, 2015

RESPIRATORY, THORACIC AND MEDIASTINAL DISORDERS - Pharyngolaryngeal pain; Pleural effusion; Pneumothorax

VASCULAR DISORDERS - Flushing; Hypotension

Rev.2/16 **NOTE**:

Sunitinib malate (SU011248 L-malate) in combination with other agents could cause an exacerbation of any adverse event currently known to be caused by the other agent, or the combination may result in events never previously associated with either agent.

